4.1 Impute Missing Adverse Events / Prior or Concomitant Medications

A. Incomplete Start Date:

Missing day and month

- If the year is the **same** as the year of the first dosing date, then the day and month of the first dosing date will be assigned to the missing fields.
- If the year is **prior to** the year of first dosing date, then December 31 will be assigned to the missing fields.
- If the year is **after** the year of first dosing, then January 1 will be assigned to the missing fields.

Missing day only

- If the month and year are the **same** as the year and month of first dosing date, then the first dosing date will be assigned to the missing day.
- If either the year of the partial date is **before** the year of the first dosing date or the years of the partial date and the first dosing date are the same but the month of partial date is **before** the month of the first dosing date, then the last day of the month will be assigned to the missing day.
- If either the year of the partial date is **after** the year of the first dosing date or the years of the partial date and the first dose date are the same but the month of partial date is **after** the month of the first dosing date, then the first day of the month will be assigned to the missing day.
- If the stop date is not missing, and the imputed start date is after the stop date, the start date will be imputed by the stop date.

Missing day, month, and year

- No imputation is needed, the corresponding AE will be included as TEAE.

B. Incomplete Stop Date:

If the imputed stop date is before the start date, then the imputed stop date will be equal to the start date.

Missing day and month

- If the year of the incomplete stop date is the **same** as the year of the last dosing date, then the day and month of the last dosing date will be assigned to the missing fields.
- If the year of the incomplete stop date is **prior to** the year of the last dosing date or prior to the year of the first dosing date, then December 31 will be assigned to the missing fields.

- If the year of the incomplete stop date is **prior to** the year of the last dosing date but is the same as the year of the first dosing date, then the first dosing date will be assigned to the missing date.
- If the year of the incomplete stop date is **after** the year of the last dosing date, then January 1 will be assigned to the missing fields.

Missing day only

- If the month and year of the incomplete stop date are the **same** as the month and year of the last dosing date, then the day of the last dosing date will be assigned to the missing day.
- If either the year of the partial date is **not equal to** the year of the last dosing date or the years of the partial date and the last dosing date are the same but the month of partial date is **not equal to** the month of the last dosing date, then the last day of the month will be assigned to the missing day.

4.2 Imputing Missing Prior/Concomitant Procedures

Prior/concomitant procedures are defined as surgeries and transplants such as stem-cell transplants.

Partially missing start/stop dates for prior/concomitant procedures will be imputed in the analysis dataset for prior/concomitant procedures. If the stop date is complete with no missing year, month, or day, and the partially missing start date imputed by the rule below is after the stop date, then the start date will be imputed by the stop date.

Partially missing prior/concomitant procedure start dates will be imputed by the earliest possible date given the non-missing field(s) of the date.

Partially missing prior/concomitant procedure stop dates will be imputed by the latest possible date given the non-missing field(s) of the date.

4.3 Imputing Missing Medical History

Partially missing medical history start dates will be imputed in the derived dataset for medical history. The 16th of the month will be used to impute a partially missing start date that has only the day missing, and July 1st will be used to impute a partially missing start date that has both the month and day missing. Should the imputed date equal or exceed the informed consent/assent date, the imputed medical history date will be set to 1 day prior to the informed consent/assent date.

4.4 Imputing Missing Disease Progression Date

If the day of the disease progression is missing, then the first day of the non-missing month will be assigned to the missing day; if the month or year of the missing date is missing, then the date will not be imputed and treated as missing.

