6. STATISTICAL METHODOLOGY FOR EFFICACY

Tables will be provided to describe the efficacy endpoints for the Response Population, Safety Population and ITT Population; the ITT Population will only be invoked if at least one of the subjects enrolled does not receive a single dose of pomalidomide. In addition, analysis of the primary endpoint, ORSDR, will be based primarily on the Response Population and decision making such as go/no-go into stage 2 will be based on the analysis using this analysis population. Tables will present data by tumor type/disease indication separately and not in aggregate. Listings will display response assessment data for the ITT Population.

Efficacy endpoints reliant on disease assessments will be based on the independent central response assessments.

In instances where disease assessments are reliant on measurements being collected over a series of days, the last day a measurement is recorded will be used as the date for documentation of the CR, PR, SD or PD.

Missing efficacy data will not be imputed.

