6.2.3. Duration of Response

Duration of response (DoR) will be presented in weeks is defined as the duration from initial response (either a CR or PR) to documented PD or death due to any cause, whichever occurs first. The response criteria should be defined in the protocol prior to the start of the study. Duration of response for subjects last known to be alive without PD is censored at the date of last adequate response assessment, or at the start of a new anticancer therapy, whichever occurs first.

The underlying analysis population is confined to those who have responded.

For identification of PD for this endpoint, PD is classified as either a PD as observed during a response assessments (both during the Treatment Period and the Follow-up Period if applicable), or as a PD as recorded on the treatment discontinuation and/or the study discontinuation eCRF; the first time this occurrence is observed is selected as the PD date.

Duration of response will be summarized by median DoR time, along with the corresponding 95% CI, calculated using Kaplan-Meier methods (the estimate of variance will be calculated using Greenwood's formula) ([Kaplan and Meier, 1958](#)) for each tumor type/disease indication separately. The Kaplan-Meier curve for DoR will be presented graphically. The proportion remaining progression/death free at 3, 6, 9, 12, 18, and 24 months will be reported and the corresponding standard error provided.

Due to the low anticipated number of subjects and events/censoring, additional summary statistics will be provided, including the arithmetic mean, median, standard deviation (StdDev), first quartile (Q1), third quartile (Q3), minimum (Min), and maximum (Max) values.

Disease assessments recorded on or after start of a new anticancer therapy will not be considered, nor will disease assessments reported after a PD has been observed.

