6.2.4. Progression-free Survival

Progression-free survival (PFS) will be presented in weeks and is defined as the time from the date of first pomalidomide dose until the date a PD is first observed or date of death (any cause), whichever occurs first. Subjects who do not have a PD or have not died at the time of an analysis will be censored at the time of their last disease assessment or at the time of start of new anticancer therapy, whichever occurs first.

For the purpose of identification of a PD for this endpoint, PD is classified as either a PD as observed during a response assessments (both during the Treatment Period and the Follow-up Period if applicable), or as a PD as recorded on the Disposition – Treatment and/or the Disposition – Follow-up eCRF; the first time this occurrence is observed is selected as the PD date.

Progression-free survival will be summarized by median progression-free time along with the corresponding 95% CI, calculated using Kaplan-Meier methods (the estimate of variance will be calculated using Greenwood's formula) ([Kaplan and Meier, 1958](#)) for each tumor type/disease indication separately. The Kaplan-Meier curves for PFS will be presented graphically. The number and percentage of total disease progression/deaths, as identified for PFS events will be summarized. The proportion remaining progression/death free at 3, 6, 9, 12, 18, and 24 months will be reported and the corresponding standard error provided.

Due to the low anticipated number of subjects and events/censoring, additional summary statistics will be provided, including the arithmetic mean, median, StdDev, Q1, Q3, Min, and Max values.

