APPENDIX A2 – CONVENTIONS RELATED TO DATES

Following are the general conventions for various computations and imputations for references. Users may need to consult with study team for specific study practices or regulatory guidelines.

1. Handling of Dates

Dates will be stored as numeric variables in the SAS analysis files and reported in DDMMYY format (ie, the Date9. date format in SAS). Dates in the clinical database are classified into the categories of procedure dates, log dates, milestone dates, outcome dates, and special dates.

- **Procedure Dates** are the dates on which given protocol-specified procedure are performed. They include the dates of laboratory testing, physical examinations, tumor scans, etc. They should be present whenever data for a protocol-specified procedure are present and should only be missing when a procedure are marked as NOT DONE in the database. Procedure dates will not be imputed.
- **Log Dates** are dates recorded in eCRF data logs. Specifically, they are the start and end dates for adverse events and concomitant medications/procedures. They should not be missing unless an event or medication is marked as *ongoing* in the database. Otherwise, incomplete log dates will be imputed according to the rules in section 4.1 and section 4.2 of this Appendix. However, in listings, log dates will be shown as recorded without imputation.
- **Milestone Dates** are dates of protocol milestones such as randomization, study drug start date, study drug termination date, study closure date, etc. They should not be missing if the milestone occurs for a subject. They will not be imputed.
- **Outcome Dates** are dates corresponding to study endpoints such as survival, progression, etc. In most cases they are derived either from a milestone (eg, the survival date is derived from the death date), or a procedure date (eg, the progression date is derived from the date of the tumor scan that was used to determine progression). They may be subject to endpoint-specific censoring rules if the outcome did not occur, but are not otherwise subject to imputation.
- **Special Dates** cannot be classified in any of the above categories and they include the date of birth. They may be subject to variable-specific censoring and imputation rules.

Dates recorded in comment fields will not be imputed or reported in any specific format.

2. Calculations Using Dates

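### SAP Appendix A2 4.4 dates a day-missing progression to the 1st of the month with no lower bound, against two other SAP statements, so PFS or DoR can come out negative or falsely short; a progression with no month has no stated analysis

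*SAP*

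**What the plan says.** Appendix A2 Section 4.4 has two rules. For a missing day: "If the day of the disease progression is missing, then the first day of the non-missing month will be assigned to the missing day". For a missing month or year: "if the month or year of the missing date is missing, then the date will not be imputed and treated as missing". Neither refers to first dose, first response or the last scan without progression.

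Two other SAP statements point the other way. Appendix A2 Section 1 classes progression among the outcome dates and says of them: "They may be subject to endpoint-specific censoring rules if the outcome did not occur, but are not otherwise subject to imputation". SAP 6 says: "Missing efficacy data will not be imputed".

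PFS (SAP 6.2.4) is "the time from the date of first pomalidomide dose until the date a PD is first observed", or death. Progression counts if seen at a response assessment "or as a PD as recorded on the Disposition – Treatment and/or the Disposition – Follow-up eCRF", and "the first time this occurrence is observed is selected as the PD date". DoR (SAP 6.2.3) starts at the first CR or PR, takes progression from the discontinuation forms in the same way, and does not use later scans: "nor will disease assessments reported after a PD has been observed".

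**The concern.** A programmer cannot follow Section 4.4, Section 1 and SAP 6 together. If 4.4 is the one followed, its day-missing rule always moves progression earlier and nothing stops it. Progression recorded for March with no day becomes 1 March, even if the first dose was on 5 March or a scan on 20 March showed PR or SD. PFS or DoR can then be negative or too short. Because the earliest source wins, an imputed date from a form also displaces a later, fully dated scan.

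The neighbouring rules in Appendix A2 Section 4 do carry guards: 4.1 checks start against stop dates, 4.2 checks the stop date, 4.3 the consent date, 4.5 consent and Cycle 1 Day 1, and 4.6 an earlier assessment. Section 4.4, which sets an efficacy event time, has none.

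The missing-month rule leaves a second gap. The PFS censoring rule covers subjects without progression or death, and the DoR rule covers those alive without progression. Neither covers a subject known to have progressed on an unknown date. PFS is read per stratum on 9 to 20 children and DoR on responders only, so single subjects matter.

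**Working it through.** The SAP states no figure on this point, so there is none to reproduce. The check takes the rule as written and applies it to the calendar.

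**1. Which dates the rule reaches.** Scan dates are procedure dates, which Appendix A2 Section 1 expects to be complete and does not impute. Section 4.4 therefore acts mainly on progression known from a form. Such cases are foreseeable:
- The end-of-treatment MRI is done only when the subject stopped for a reason other than progression (Protocol 3.1; Table 4, footnote j).
- Clinical deterioration alone is enough for progression (Protocol Appendix C, Table 10).
- Progression before the end of Cycle 1 is expected (Protocol 9.2, Response Population).

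**2. Size of the shift.** Shift = day of month − 1. Over all 1,461 dates in a four-year span the shifts sum to 21,520 days, so the mean is 21,520 / 1,461 = 14.7 days (14.7 / 7 = 2.1 weeks). The median is 15 and the maximum 30 days (4.3 weeks). The shift is never later.

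**3. When the order is reversed.** Let g be the days from a reference date (first dose, first response or last progression-free scan) to true progression. The imputed date falls before the reference when day of month − 1 > g. Share of calendar positions, given that the day is missing:

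| g (days) | imputed date before the reference |
|---|---|
| 7 | 74% |
| 14 | 51% |
| 21 | 28% |
| 28 | 5% |
| 30 or more | 0% |

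Counting ties on the reference date gives 77%, 54% and 31% at 7, 14 and 21 days.

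**4. Worked examples.**
- PFS: first dose 12 March, true progression 30 March. True PFS = 30 − 12 + 1 = 19 days. With the day missing the date becomes 1 March, which is 12 − 1 = 11 days before first dose.
- DoR: response scan 9 May, true progression 29 May. True DoR = 29 − 9 + 1 = 21 days. The imputed date, 1 May, is 9 − 1 = 8 days before the response.

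**5. How the scan schedule limits this.** Outside DIPG, scheduled brain MRIs are on Day 1 of Cycles 3, 5, 7, 10 and so on, 56 to 84 days apart. The first is at least 56 − 7 = 49 days after first dose, allowing for the window. Since reversal needs g below 30, it arises from clinical, form-recorded or unscheduled-scan progression, not from the scheduled scans. If true progression is assumed spread evenly over a 56- or 84-day interval after a clean scan, the imputed date falls before that scan in 25% or 16% of day-missing cases (26% or 18% with ties).

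**6. Missing month.** This illustration uses assumed times. Take nine subjects, all with events, at 4, 6, 8, 9, 12, 16, 20, 24 and 28 weeks. The median is 12 weeks. Five events fall by 3 months (13.0 weeks), so 3-month PFS is 4/9 = 44.4%. Suppose the 12-week progression is undated and is censored 4 weeks earlier, at week 8. Then 3-month PFS is 8/9 × 7/8 × 6/7 × 4/5 = 53.3%, and the median moves to 16 weeks. Choosing another of the nine leaves the median at 12 or moves it to 16, with 3-month PFS between 44.4% and 50.8%.

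**The case against.** The case for leaving this alone is that the trigger is narrow. Scan dates should be complete, tumor-based endpoints rest on central review (SAP 6), and Protocol 11.1 requires the date a subject came off treatment to be recorded. The percentages apply only once the day is missing and only to gaps under 30 days. Moving progression earlier also shortens PFS, which is the conservative direction in a single-arm study.

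Most of this stands as a limit on size. It does not remove the contradiction between the three SAP statements. A negative time is also unusable rather than conservative, and the missing-month gap can work in the other direction.

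Three stronger readings are tempting, and the documents do not support them:
- A reader might infer that every progression without a month is a lost event. Section 4.4 makes the date missing, not the event. A dated scan progression or a death can still supply the event, though usually later. Loss by censoring or dropping is one possible result of the SAP's silence, not an instruction.
- A reader might infer that a genuine later scan must be discarded from DoR. SAP 6.2.3 excludes assessments after an observed progression; it does not say that this is judged against an imputed date.
- A reader might infer that the stage decisions are at risk. For ORSDR, SAP 6.1.1 takes progression from response assessments only, and those dates are not imputed.

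**Conclusion.** The point holds for PFS and DoR. Section 4.4 contradicts Appendix A2 Section 1 and SAP 6. Applied as written, it can put a day-missing progression before first dose, first response or a clean scan whenever true progression is within about 30 days of that reference. The shift averages 14.7 days earlier and reaches at most 30. For PFS the realistic failure is a date before first dose; for DoR it is a date before the response scan. How a known progression with no month is analysed is not stated.

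The shares assume calendar dates spread evenly, and the Kaplan-Meier illustration uses assumed times. The documents do not say how often progression dates will be partial, so the expected effect on any stratum cannot be given. The primary endpoint and the stage decisions are essentially unaffected. The rule should be corrected before database lock because it gives a wrong result as written and is cheap to change.

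**What to change.** Change the SAP wording as follows.

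1. Amend Appendix A2 Section 1 and SAP 6 so that partial progression dates are an explicit exception to the no-imputation statements.
2. For a missing day, impute the latest of: the first day consistent with the known parts; the day after the last adequate progression-free assessment (which includes the response scan); and the day after first dose. The result may be no later than death or the end of the known month.
3. Do not cap the date at treatment discontinuation. Progression after treatment stops is expected and counted (Protocol 3.1 and 6.3.3; SAP 6.2.4). A child who stops in June, has a clean scan in December and progresses in March with the day missing would be pulled back to June, before that clean scan.
4. For a missing month, use the treatment-discontinuation date only if progression was the recorded reason for stopping. Otherwise use the next dated evidence of progression, or death. Keep the subject as an event.

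The change needs no new data and adds no work at sites. Its downside is that an affected day-missing date may be up to about 30 days later than under the current rule.

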4.5 Imputing Missing Dates for Prior Therapies

Prior therapies are defined as prior radiation therapies, prior systemic anticancer therapies, and other prior anticancer therapies. Should the imputed date equal or exceed the informed consent/assent date, the imputed start date will be set to 2 days prior to the informed consent/assent date, while the imputed end date will be set to 1 day prior to the informed consent/assent date.

A. Incomplete Start Date:

If the start day of any prior therapy date is missing, then the first day of the non-missing month will be assigned to the missing day; if month or year of the missing date is missing, then the date will not be imputed and treated as missing.

B. Incomplete End Date:

Incomplete date of end of last therapy will be imputed using the following rule: If missing day, impute 15th day of the month; if missing month, impute missing month as middle month (or the earlier month of two month if two months tie) between therapy start month and month of cycle 1 day 1. Should the imputed date be within 21 days of cycle 1 day 1, then the imputed date will be re-set to the 22nd day before cycle 1 day 1.

4.6 Imputing Missing Dates for Date of Birth

Partial birth date: impute missing day as 15th of the month; impute missing month as July; set missing age for missing year. Should the imputed age succeed an earlier assessment date collected for that subject, the imputed month will be set to the month preceding the assessment date.

APPENDIX A3 – STUDY SPECIFICS

CELGENE PROPRIETARY INFORMATION

Table 3: Table of Events

Period	Protocol Reference Section	Screening Period	Treatment Period ^b							Follow-up Period ^b		
		Screening ^a	Each 28-day Cycle						End of Treatment (± 3 days)	28-Day Post Treatment Safety Follow-up	Long-term Follow-up (± 14 days)	
			Cycles 1 - 2 (± 3 days)				Cycles 3 - 12 (± 3 days) ⁱ					Cycles 13 - 24 (± 3 days) ⁱ
Day		-28 to 0	1	8	15	22	1	15	1			
Study Entry and General Assessments												
Obtain Informed Consent/Assent	13.3	X	-	-	-	-	-	-	-	-	-	-
Interactive Response Technology	7.3	X	X	-	-	-	X	-	X	X	-	-
Enrollment	6.1.5	-	X ^o	-	-	-	-	-	-	-	-	-
Demographics	6.1.2	X	-	-	-	-	-	-	-	-	-	-
Inclusion/Exclusion Criteria	4.2, 4.3	X	X ^o	-	-	-	-	-	-	-	-	-
Complete Medical History	6.1.3	X	-	-	-	-	-	-	-	-	-	-
Prior Disease Therapies and History	6.1.4	X	-	-	-	-	-	-	-	-	-	-
Prior/Concomitant Medication and Procedures	8.0	After signing ICF/IAF and until 28-day post-treatment Safety Follow-up Visit										-
Safety Assessments												
Adverse Events	10	After signing ICF/IAF and until 28-day post-treatment Safety Follow-up Visit										-
Assessment of Second Primary Malignancy	6.2.4.10	After signing ICF/IAF and until end of Long-term Follow-up Visit										
Physical Exam (including vital signs)	6.4.2.1	X	X ^e	-	-	-	X	-	X	X	X	-
Pomalidomide Education and Counseling ^d	6.4.2.9	X	X	-	-	-	X	-	X	X	X	-
Height	6.4.2.2	X	X	-	-	-	X	-	X	X	X	-

Period	Protocol Reference Section	Screening Period	Treatment Period ^b							Follow-up Period ^b		
		Screening ^a	Each 28-day Cycle						End of Treatment (± 3 days)	28-Day Post Treatment Safety Follow-up	Long-term Follow-up (± 14 days)	
			Cycles 1 – 2 (± 3 days)				Cycles 3 - 12 (± 3 days) ⁱ					Cycles 13 - 24 (± 3 days) ⁱ
Day		-28 to 0	1	8	15	22	1	15	1			
Body Weight	6.4.2.3	X	X	-	-	-	X	-	X	X	X	-
BSA calculation	Error! Reference source not found.	X	X	-	-	-	X	-	X	-	-	-
Lansky/Karnofsky Performance Status	Error! Reference source not found.	X	X	-	-	-	X	-	X	X	X	-
Hematology ^e	6.4.2.6	X	X ^c	X	X	X	X	X	X	X	X	-
Serum blood chemistry ^e	6.4.2.6	X	X ^c	X	X	X	X	X	X	X	X	-
Hepatitis B serology (if applicable)	6.4.2.6	X	-	-	-	-	-	-	-	-	-	-
Pulse oximetry (O ₂ saturation)	6.4.2.7	X	As clinically indicated									-
Serum or Urine β-hCG Testing (FCBP/FCCBP) ^f	6.4.2.9	X ^g	X ^g	X ^o	X ^o	X ^o	X	-	X	X	X	-
Neurological assessment	6.4.2.8	X	X	-	-	-	X	-	X	X	X	-
Treatment Administration, Accountability and Compliance												
Pomalidomide Dispensing	7.2	-	X	-	-	-	X	-	X	-	-	-
Pomalidomide Administration	7.2	-	Days 1-21			-	Days 1-21		Days 1-21		-	-

Period	Protocol Reference Section	Screening Period	Treatment Period ^b							Follow-up Period ^b		
		Screening ^a	Each 28-day Cycle							End of Treatment (± 3 days)	28-Day Post Treatment Safety Follow-up	Long-term Follow-up (± 14 days)
			Cycles 1 – 2 (± 3 days)				Cycles 3 - 12 (± 3 days) ⁱ		Cycles 13 - 24 (± 3 days) ⁱ			
Day		-28 to 0	1	8	15	22	1	15	1			
Response Assessments (High-grade glioma, Medulloblastoma and Ependymoma)												
Brain MRI with and without gadolinium	6.4.1	X ^h	-	-	-	-	Day 1 of Cycles 3, 5, 7, 10, 13, 16, 19, 22 and after Cycle 24 ⁱ			X ^j	-	X ^k
Spine MRI with gadolinium	6.4.1	X ^h	-	-	-	-	Day 1 of Cycles 3, 5, 7, 10, 13, 16, 19, 22 and after Cycle 24 ⁱ			X ^j	-	X ^k
Cerebrospinal fluid cytology	6.4.1	As clinically indicated ^m										
Response Assessments (DIPG)												
Brain MRI with and without gadolinium	6.4.1	X ^h	-	-	-	-	Day 1 of Cycles 4, 7, 10, 13, 16, 19, 22 and after Cycle 24 ⁱ			X ^j	-	X ^k
Spine MRI with gadolinium	6.4.1	X ^h	-	-	-	-	Day 1 of Cycles 4, 7, 10, 13, 16, 19, 22 and after Cycle 24 ⁱ			X ^j	-	X ^k
Cerebrospinal fluid cytology	6.4.1	As clinically indicated ^m										
Pharmacokinetics – Optional												
Optional Pharmacokinetic blood sampling	6.5	-	-	X ^o	X ^o	-	-	-	-	-	-	-
Follow-up												
PFS, DoR, OS, drug related SAEs, SPMs, new anticancer therapies	6.3	-	-	-	-	-	-	-	-	-	-	X ⁿ

β-hcg = beta human chorionic gonadotropin; BSA = body surface area; DoR = duration of response; IAF = informed assent form; ICF = informed consent form; MRI = magnetic resonance imaging; O₂ = oxygen; OS = overall survival; PFS = progression free survival; SAE = serious adverse event; SPM = second primary malignancy.

^a Clinical evaluations to establish eligibility can be obtained up to 28 days prior to Cycle 1, Day 1 (first dose of study drug) unless noted otherwise. Brain/Spine MRI assessments can be obtained up to 21 days prior to Cycle 1, Day 1. Assessments should be re-evaluated as needed if there is a change in clinical status.

^b Deviations within the provided study visit windows are allowed unless noted otherwise for a particular assessment.

^c Safety laboratory (hematology and serum blood chemistry) and physical examinations do not need to be repeated on Cycle 1, Day 1 if performed within 7 days of starting treatment, unless clinically indicated. FCBP/FCCBP must have pregnancy test performed within 24 hours prior to the initial dosing of pomalidomide.

^d Can also be conducted verbally via phone from the site. Subjects must also be counseled against sharing pomalidomide and donating blood, semen or sperm during therapy until the 28-day post-treatment Safety Follow-up Visit. Pregnancy counseling and potential risks must be conducted on Day 1 of each cycle prior to pomalidomide dispensing or at a minimum of every 28 days during the Treatment Period.

- ^e Subjects who experience toxicity should have appropriate laboratory testing at least twice weekly (3 to 4 days apart or more frequently) until the toxicity has resolved.
- ^f Testing with a sensitivity of at least 25 mIU/mL will be performed in FCBP/FCCBP subjects; refer to Section 6.4.2.9 of the protocol for details. The subject may not receive pomalidomide until the Investigator has verified that the result of the pregnancy test performed on Day 1 (within 24 hours prior to treatment) of every cycle is negative.
- ^g Obtain 10 to 14 days prior to first dose of study drug and again within 24 hours prior to first dose of study drug. **NOTE:** The pregnancy test 10 to 14 days prior to initiation of pomalidomide may be omitted, at the discretion of the investigator, for any FCCBP/FCBP who has high acuity disease requiring immediate treatment with pomalidomide. The pregnancy test within 24 hours prior to the first dose of pomalidomide is required to be performed.
- ^h Screening/baseline MRI can be obtained up to 21 days prior to Cycle 1 Day 1.
- ⁱ Brain/Spine MRIs can be performed within 7 days prior to scheduled timepoint.
- ^j Response/MRI assessment will be performed at the End of Treatment Visit only if the subject has discontinued for reasons other than PD and has been more than 8 weeks since their most recent scan/response assessment.
- ^k Subjects that discontinue treatment prior to disease progression will be followed with MRI tumor assessments every 6 months from treatment discontinuation for the first year off treatment, then annually thereafter until PD, start of a new anticancer therapy, consent/assent is withdrawn, is lost to follow-up, or death.
- ^l If no spinal or leptomeningeal disease is present at screening/baseline, subsequent spine MRIs will be obtained on Day 1 of Cycle 7, 13, 19 (or within 7 days prior to dosing), after completion of Cycle 24 (\pm 3 days) and as clinically indicated at the discretion of the primary treating physician. If there is spinal or leptomeningeal disease present at screening/baseline, spine MRIs will be obtained at the same time points as the brain MRI.
- ^m As clinically indicated to follow disease at the discretion of the primary treating physician. It is recommended to follow at the same interval as required MRIs if positive at screening/baseline.
- ⁿ SPMs should be reported regardless of causality. After treatment discontinuation, all subjects will be followed every 3 months from the 28-Day post-treatment Safety Follow-Up Visit for up to 5 years after the last subject enrolled.
- ^o Cycle 1 only

1. Performance Status

Table 4: Performance Status

Karnofsky Scale (age ≥ 16 years)		Lansky Scale (age < 16 years)	
Able to carry on normal activity and to work; no special care needed.		Able to carry on normal activity; no special care is needed	
100	Normal no complaints; no evidence of disease	100	Fully active
90	Able to carry on normal activity; minor signs or symptoms of disease	90	Minor restriction in physically strenuous play
80	Normal activity with effort; some signs or symptoms of disease	80	Restricted in strenuous play, tires more easily, otherwise active
Unable to work; able to live at home and care for most personal needs; varying amount of assistance needed.		Mild to moderate restriction	
70	Cares for self; unable to carry on normal activity or to do active work	70	Both greater restrictions of, and less time spent in active play
60	Requires occasional assistance, but is able to care for most of his personal needs	60	Ambulatory up to 50% of the time, limited active play with assistance/supervision
50	Requires considerable assistance and frequent medical care	50	Considerable assistance required for any active play, fully able to engage in quiet play
Unable to care for self; requires equivalent of institutional or hospital care; disease may be progressing rapidly.		Moderate to severe restriction	
40	Disabled; requires special care and assistance	40	Able to initiate quiet activities
30	Severely disabled; hospital admission is indicated although death not imminent	30	Needs considerable assistance for quiet activity
20	Very sick; hospital admission necessary; active supportive treatment necessary	20	Limited to very passive activity initiated by others (eg, television)
10	Moribund; fatal processes progressing rapidly	10	Completely disabled, not even passive play
0	Dead	0	Unresponsive

Source: Karnofsky, 1949; Lansky 1987.

2. Blood Collection for Pharmacokinetic Analysis

Sparse whole blood samples for PK analysis will be collected from consenting subjects at the time points specified in [Table 5](#): PK Sampling Schedule During Cycle 1 Day 1. Blood samples MUST be drawn from the arm contra lateral to the arm with the intravenous infusion of concomitant medications (if applicable). For each PK sample, draw approximately 1 mL blood and prepare plasma by centrifugation at 4°C. The dose of pomalidomide (Cycle 1: Day 8 and 15) should be administered to subjects in the morning at the study center after the collection of the pre-dose PK blood samples. To reduce PK variability on PK sampling days, subjects will be asked not to eat for 2 hours prior and 2 hours after pomalidomide administration.

Table 5: PK Sampling Schedule During Cycle 1 Day 1

Collection Time Relative to Pomalidomide Administration	Collection Window	Cycle 1, Day 8	Cycle 1, Day 15
0 hour (pre-dose)	-90 min	x	x
2 hours	± 30 min	x	x
